### **4.2. Study Design Rationale**

Crossover designs are a well-established cost-effective study design in which subjects are exposed to multiple treatments during different time periods. This design was considered because patient-specific factors that might affect comfort are well controlled. A washout period of 7-9 days was implemented between each treatment exposure to reduce any potential carry-over effect that may bias the results.

### **4.3. Enrollment Target and Study Duration**

A total of up to 60 subjects will be enrolled (informed consent signed) at a single clinical site (University of Manchester) in the UK. The goal is for a sample size of approximately 50 subjects after subjects who withdraw or are lost to follow-up.

The Investigator is responsible for ensuring that all subjects entering the study conform to subject selection criteria. The number of subjects targeted for randomization and completion are as follows:

Table 1: Target number of subjects by arm and site

	Test/Control	Control/Test	Total
Randomization	30	30	60
Completion	25	25	50
Number of sites			1
Number of subjects/site Min-Max	25-30	25-30	50-60

The study will last approximately 3 months and include a 2-month enrollment period.

Once the informed consent has been signed the subject will be considered enrolled.

An additional subject may be enrolled if a subject discontinues from the study prematurely.

## 5. TEST ARTICLE ALLOCATION AND MASKING

### 5.1. Test Article Allocation

Eligible subjects will sequentially try the Test and Control eye drops in a random order. A computer-generated randomization scheme will be used to randomly assign subjects, in block size of 2, to one of the two possible treatment sequences: Test/Control or Control/Test.

The study site will follow the randomization scheme provided and will complete enrollment according to the randomization list and will not pre-select or assign subjects. The assignment of the subjects must be performed at the first baseline visit (Visit 1). The following must have occurred prior to randomization:

- Informed consent has been obtained
- Subject meets all the inclusion / exclusion criteria
- Subject history and baseline information has been collected

The randomization scheme will be generated using the PROC PLAN procedure from the SAS Software Version 9.4 or higher (SAS Institute, Cary, NC).

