### 5.2. Masking

This is a double-masked study where subjects, investigators are masked to the identity of the eye drops during the study period. Every attempt will be made to keep the other clinical trial personnel involved in the study (e.g., Data management, Biostatistician) unaware of the identity of the test articles.

The identity of the investigational products will be masked by over labeling the eye drop bottles with a label containing the study number, expiration date and the randomization codes. Only the personnel involved in the over labeling and the Statistician generating the randomization scheme will have access to the decode information translating the randomization codes into Test and Control treatment. The medical monitor will also have access to the decode information in case breaking the mask is necessary for the urgent medical treatment of a subject.

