### 5.3. Procedures for Maintaining and Breaking the Masking

Under normal circumstances, the mask should not be broken until all subjects have completed the study and the database is finalized. Otherwise, the mask should be broken only if specific emergency treatment/course of action would be dictated by knowing the treatment status of the subject. In such cases, the Investigator may, in an emergency, contact the medical monitor. In the event the mask is broken, the Sponsor must be informed as soon as possible. The date, time, and reason for the unmasking must be documented in the subject record. The Investigator is also advised not to reveal the study treatment assignment to the clinical site or Sponsor personnel.

When dispensing test articles, the following steps should be followed to maintain randomization codes:

1. Investigator or designee (documented on the Delegation Log) will consult the randomization scheme to obtain the test article assignment for that subject prior to dispensing
2. Investigator or designee will record the subject's number on the appropriate line of the randomization scheme
3. Investigator or designee will pull the appropriate test articles from the study supply. All test articles that are opened, whether dispensed (placed/fit on eye or dispensed outside the clinical site) or not, must be recorded on the Test Article Accountability Log in the "Dispensed" section

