#### 8.2. Withdrawal/Discontinuation from the Study

A subject will be withdrawn from the study for any of the following reasons:

- Subject death during the study period
- Subject withdrawal of consent
- Subject not compliant to the study protocol including drop usage schedule
- Subject lost to follow-up
- Subject no longer meets eligibility criteria (e.g. the subject becomes pregnant)
- Subject develops significant or serious adverse events causing discontinuation of study drop
- Subjects who have experienced a Corneal Infiltrative Event (CIE)

- Investigator's clinical judgment regarding the subject safety reasons (that it is in the best interest of the subject to stop treatment)
- Subject not successfully dispensed due to lack of efficacy or safety

For discontinued subjects, the Investigator will:

- Complete the current visit (scheduled or unscheduled)
- Complete the Final Evaluation, indicating the reason that the subject was discontinued from the study
- Collect used test article(s) (brought to the visit) from the subject and discard them, unless otherwise stated in Section 7.2
- Collect all unused test article(s) from the subject

An additional subject may be enrolled if a subject discontinues from the study prematurely.

In cases where a subject is lost to follow-up, every possible effort must be made to contact the subject and determine the reason for discontinuation/withdrawal. The measures taken to follow up must be documented including two written attempts and a certified letter (or equivalent) as the final attempt.

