### 13.2.1. Causality Assessment

**Causality Assessment** – A determination of the relationship between an adverse event and the test article. The test article relationship for each adverse event should be determined by the investigator using these explanations:

- Not Related- An adverse event that is not related to the use of the test article, study treatment or study procedures
- Unlikely Related – An adverse event for which an alternative explanation is more likely, e.g. concomitant treatment, concomitant disease(s), or the relationship of time suggests that a causal relationship is not likely
- Possibly Related – An adverse event that might be due to the use of the test article, or to the study treatment or study procedures. An alternative explanation, e.g. concomitant treatment, concomitant disease(s), is inconclusive. The relationship in time is reasonable. Therefore, the causal relationship cannot be excluded
- Related – An adverse event that is listed as a possible adverse effect (device) or adverse reaction (drug) and cannot be reasonably explained by an alternative explanation, e.g. concomitant treatment of concomitant disease(s). The relationship in time is very suggestive, e.g. it is confirmed by de-challenge and re-challenge

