#### **13.4.1. Reporting Adverse Events to Sponsor**

##### **Serious/Significant Adverse Events**

The Investigator will inform the sponsor of all serious/significant adverse events occurring during the study period as soon as possible by e-mail, fax, or telephone, but no later than 24 hours following discovery of the event. The Investigator is obligated to pursue and obtain information requested by the Sponsor in addition to that information reported on the eCRF. All subjects experiencing a serious/significant adverse event must be followed up and all outcomes must be reported.

When medically necessary, the Investigator may break the randomization code to determine the identity of the treatment that the subject received. The Sponsor and study monitor should be notified prior to unmasking the test articles.

In the event of a serious/significant adverse event, the Investigator must:

- Notify the Sponsor immediately
- Obtain and maintain in the subject's records all pertinent medical information and medical judgment for colleagues who assisted in the treatment and follow-up of the subject
- Provide the Sponsor with a complete case history which includes a statement as to whether the event was or was not related to the use of the test article
- Notify the IEC/IRB as required by the IEC/IRB reporting procedure according to national regulations

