#### **14.7. Other Exploratory Analyses**

If superiority cannot be concluded, the predictive probability of trial success (PPOS) will be calculated for different scenarios of sample size ( $n$ ) to support the planning for future studies.

Given the historical data from this pilot study, the PPOS will be estimated using a simulation based algorithm. We will simulate 1000 trials of 120 subjects from the predictive density function of  $y$ , then we will assess if success criterion  $\beta_3 > 0$  is met for each trial. The PPOS is estimated by the proportion of runs where the success criterion is met. The same algorithms will be used to calculate the PPOS for  $n = 150, 200$ .

Further exploratory analysis will be conducted on DEQ-5 scores, LipiView II® lipid layer measurements, non-invasive tear break-up time (NITBUT), corneal staining and subject's reported ocular symptoms (CTP-2009) at the discretion of the Study Responsible Clinician.

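### A fixed, disclosed block size of 2 at one site lets a single code break also reveal the block partner's sequence: minor, and cheap to improve

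*Combined protocol and SAP*

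**What the plan says.** **Allocation.** Section 5.1: "A computer-generated randomization scheme will be used to randomly assign subjects, in block size of 2", to Test/Control or Control/Test. Table 1 in Section 4.3 targets 30 subjects per sequence at one site, and Section 4.3 adds: "The study will last approximately 3 months and include a 2-month enrollment period". No stratification, variation of block size or withholding of block size from the site is described. Under Section 5.3, site staff consult the scheme before dispensing and write each subject's number "on the appropriate line of the randomization scheme".

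**Masking and code breaks.** Section 5.2 masks subjects and investigators. The decode is held by the over-labeling staff and the statistician who generates the scheme, and "The medical monitor will also have access to the decode information". Section 5.3 limits breaks to emergencies in which knowing the treatment would dictate care, routes the request through the medical monitor, and advises the investigator not to pass the assignment on. Section 13.4.1 says that, when medically necessary, "the Investigator may break the randomization code to determine the identity of the treatment that the subject received". Section 11 lets the sponsor unmask after certain serious events and discuss this with the investigator.

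**Labels.** Section 5.2 puts the randomization code on the bottle. Section 6.4 adds product code, lot number and expiry date. Neither section says whether codes are unique to a subject or shared by product, or whether the lot and product codes are masked.

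**Primary model.** Section 14.5 has sequence and solution as fixed effects, plus baseline. It has no period term.

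**The concern.** With two sequences in a block of 2, one member's assignment determines the other's. The investigator has the block size from the protocol and the list order from the scheme, so block boundaries can be read off directly. A break made for one subject's care then unmasks a second subject who had no emergency or, if the partner is not yet randomized, reveals the next allocation.

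The partner matters more than the subject whose code was broken. That subject may well leave the study, since Section 8.2 lists as a withdrawal reason: "Subject develops significant or serious adverse events causing discontinuation of study drop". The partner normally stays and goes on being assessed by someone who now knows the product in each period. The measures open to influence are those the investigator judges: NITBUT timed by stopwatch (Appendix E), slit-lamp and staining grades, and adverse event causality, on which Section 13.2.1 says: "The test article relationship for each adverse event should be determined by the investigator". Causality is the most sensitive, because a break prompted by a suspected product reaction could color the reading of the partner's events.

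The unmasked subject's own other period is not counted here. Any two-period crossover reveals it, whatever the block size.

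**Working it through.** **Inputs.** Block size 2 and two sequences (5.1); 60 subjects, 30 per sequence, one site, target of 50 completers (Table 1); enrollment over 2 months (4.3); treatment periods of 7 to 9 days (4.1). The number of code breaks is not given; 0 to 2 is assumed.

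**1. Table 1.** 60/2 = 30 blocks, each holding one subject per sequence, gives 30 and 30, as stated.

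**2. What one known assignment says about a block-mate.** In a block of size 2m, P(another member has the opposite sequence) = m/(2m − 1).
- Size 2: 1/1 = 1.00
- Size 4: 2/3 = 0.67
- Size 6: 3/5 = 0.60

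With no information the figure would be 0.50.

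**3. Mixed blocks with hidden boundaries.** Take six blocks of 4 and six of 6: 24 + 36 = 60 subjects, 12 + 18 = 30 per sequence. Of the 59 adjacent pairs in the list, 6 × 3 = 18 lie within blocks of 4, 6 × 5 = 30 within blocks of 6, and 11 straddle two blocks. P(neighbour opposite) = (18 × 2/3 + 30 × 0.60 + 11 × 0.50)/59 = (12 + 18 + 5.5)/59 = 0.602. Simulation gives 0.60.

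**4. Extra disclosure per break.** One partner × 2 periods = 2 of 120 planned treatment periods = 1.7%. With 0 to 2 breaks: 0 to 2 partners, at most 4/120 = 3.3%. This presumes subject-unique codes and uninformative labels.

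**5. How often the next allocation is exposed.** Assume even accrual, a break equally likely on any treatment day, and a probability of 0.5 that the unmasked subject is first in the block. The partner is then still unrandomized with probability 0.5 × gap/treatment days. Sixty subjects over about 60 days gives a 1-day gap, so with two 8-day periods 0.5 × 1/16 = 3.1%. The range is 0.5 × 0.5/18 = 1.4% to 0.5 × 3/14 = 10.7%. Usually, then, the partner is already in the study. These figures are conditional on a break that may never happen.

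**6. What larger blocks cost.** If enrollment stops mid-block, the largest sequence imbalance is 1 with blocks of 2 and 3 with a block of 6.
- *Without a period term.* The treatment difference is in effect the mean of the within-subject Test − Control differences (baseline covariate left aside), and it carries the share (n1 − n2)/(n1 + n2) of any period effect. At 27:24 this is 3/51 = 5.9%; at 26:25 it is 1/51 = 2.0%.
- *With a period term.* That share is zero, and the cost is variance: (1/26 + 1/24)/(1/25 + 1/25) = 1.0016 at 50 subjects and (1/27 + 1/24)/(1/26 + 1/25) = 1.0031 at 51, an increase of 0.2% to 0.3%.
- *For scale.* If the 10 losses allowed for in Table 1 fall at random on 30:30, the number lost from one sequence has variance 10 × 0.25 × 50/59 = 2.12, so the imbalance has SD 2 × √2.12 = 2.9. Drop-out alone can produce an imbalance of this order at any block size.

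**The case against.** **The effect may not be due to block size.** If randomization codes are shared by product, or if the lot, expiry or product code on the label identifies the product, one break tells the site about every subject with that code or lot. Block size then adds nothing, and larger blocks alone would change nothing. This stands. The documents do not settle the matter, so it is a condition on both the size of the effect and the remedy.

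**Safeguards exist.** Breaks are for emergencies only, in a study of two marketed over-the-counter tears used for about a week each, and the investigator is advised to keep the assignment private. This stands as a reason to expect few breaks and little onward spread. It does not stop the investigator's own inference about the partner.

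**The trial is an exploratory pilot.** The exposed efficacy measures are analyzed "at the discretion of the Study Responsible Clinician". This also stands, and it limits the rating.

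**The remedy is not free.** Close sequence balance protects a primary model without a period term, so the cost would fall on the primary endpoint while the gain falls on exploratory measures. This is correct but small, arises only if enrollment stops mid-block, and disappears with a period term.

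**Two stronger readings are tempting.**
- A reader might infer that the primary comparison is at risk. VAS comfort and OSDI are answered by the subjects, who learn nothing from a break in another subject's code, so the documents do not support that.
- A reader might also take Section 13.4.1 as a second, direct route by which the investigator opens the code. Section 5.2 does not give the investigator the decode, so in practice the request goes through the medical monitor under Section 5.3. A cross-reference would be clarification only and forms no part of this point.

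**Conclusion.** The point holds as a minor one. With block size 2 printed in the protocol and the list kept at the one site, a break reveals the block partner's sequence with certainty, where mixed blocks of 4 and 6 would leave a guess that is right about 60% of the time. The extra exposure is one subject and 1.7% of treatment periods per break.

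That size rests on subject-unique codes and on labels that do not identify the product. If either fails, a break reveals more than the partner whatever the block size. It also rests on an assumed 0 to 2 breaks; with none, there is no effect. What is exposed is investigator-judged exploratory measures and adverse event causality. No tested hypothesis depends on them.

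**What to change.** 1. In Section 5.1, replace the fixed block size with randomly mixed permuted blocks whose sizes are held by the randomization statistician and not disclosed to the site. Six blocks of 4 and six of 6 in random order keep 30:30. The sizes belong in the statistician's specification, not in the protocol.
2. In Sections 5.2 and 6.4, state that randomization codes are unique to each subject and that lot and product codes on the label are masked, with expiry dates that do not separate the products. Without this, the first change may have no effect.
3. Preferably add a period term to the model in Section 14.5, which removes the one statistical downside.

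**Cost.** One re-run of PROC PLAN before the first randomization, short wording changes, and label preparation to match; no added subjects or visits. If enrollment stops mid-block, the maximum imbalance rises from 1 to 3. Without a period term, up to about 6% of any period effect could enter the Test − Control difference, against about 2% at an imbalance of 1. With a period term, the cost is 0.2% to 0.3% in variance at 50 to 51 subjects.

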### 5.2. Masking

This is a double-masked study where subjects, investigators are masked to the identity of the eye drops during the study period. Every attempt will be made to keep the other clinical trial personnel involved in the study (e.g., Data management, Biostatistician) unaware of the identity of the test articles.

The identity of the investigational products will be masked by over labeling the eye drop bottles with a label containing the study number, expiration date and the randomization codes. Only the personnel involved in the over labeling and the Statistician generating the randomization scheme will have access to the decode information translating the randomization codes into Test and Control treatment. The medical monitor will also have access to the decode information in case breaking the mask is necessary for the urgent medical treatment of a subject.

### 5.3. Procedures for Maintaining and Breaking the Masking

Under normal circumstances, the mask should not be broken until all subjects have completed the study and the database is finalized. Otherwise, the mask should be broken only if specific emergency treatment/course of action would be dictated by knowing the treatment status of the subject. In such cases, the Investigator may, in an emergency, contact the medical monitor. In the event the mask is broken, the Sponsor must be informed as soon as possible. The date, time, and reason for the unmasking must be documented in the subject record. The Investigator is also advised not to reveal the study treatment assignment to the clinical site or Sponsor personnel.

When dispensing test articles, the following steps should be followed to maintain randomization codes:

1. Investigator or designee (documented on the Delegation Log) will consult the randomization scheme to obtain the test article assignment for that subject prior to dispensing
2. Investigator or designee will record the subject's number on the appropriate line of the randomization scheme
3. Investigator or designee will pull the appropriate test articles from the study supply. All test articles that are opened, whether dispensed (placed/fit on eye or dispensed outside the clinical site) or not, must be recorded on the Test Article Accountability Log in the "Dispensed" section

## 6. STUDY INTERVENTION

### 6.1. Identity of Test Articles

Table 2: Artificial Tears

	Test	Control
Solution Name/Description	blink® intensive TRIPLE ACTION 3 in 1 eye drops	Systane® BALANCE eye drops
Manufacturer	Johnson & Johnson Vision, Inc	Alcon
Ingredients	liposomes, sodium hyaluronate, vitamin E polyethylene glycol succinate (TPGS), polyethylene glycol 400 (PEG 400), disodium edetate, polyhexanide methylbiguanide and purified water.	Propylene Glycol 0.6%, boric acid, dimyristoyl phosphatidylglycerol, edetate disodium, hydroxypropyl guar, mineral oil, polyoxyl 40 stearate, POLYQUAD® (polyquaternium-1) 0.001% preservative, sorbitan tristearate, sorbitol and purified water. May contain hydrochloric acid and/or sodium hydroxide to adjust pH.
Packaging Form	Over-Labeled	Over-Labeled

## 6.2. Ancillary Supplies/Products

The following solutions will be used in this study:

Table 2: Ancillary Supplies

Solution Name/Description	Solution	
	Saline Pods	Fluorescein Strips
Manufacturer	BlueDot (or alternative Sponsor-approved product)	Contacare Ophthalmics and Diagnostics (or alternative Sponsor-approved product)
Preservative	None	None
Other distinguishing items (dye, packaging, approval status, etc.)	NA	100 strips, CE marked

Sodium fluorescein dye will be used for biomicroscopy, as needed. Sterile, preservative-free, single-use eye wash (0.9% w/v sodium chloride solution) will be used in this clinical study to rinse each eye.

## 6.3. Administration of Test Articles

Test articles will be dispensed to subject meeting all eligibility requirements, including any dispensing requirements set forth in this clinical protocol. Subjects will be dispensed an adequate supply of test articles to complete the study. Lost or damaged test articles will not be replaced at the discretion of the Investigator and/or the Sponsor.

## 6.4. Packaging and Labeling

The test articles will be packaged in bottles as the primary packaging. The test article will be over-labeled to mask the subject to the identity. The test articles will be in investigational cartons sealed with a tamper evident seal, commercial cartons, or in plastic bags as the secondary packaging form. The labels for the primary and secondary packages will contain the following message, in accordance with JJV over-labeling procedures for masked studies involving marketed products: “For Use in Clinical Study CR-6013 Only, Not for Resale. Product Conforms to with CE Mark Requirements.” The labels will also contain the product code, lot number, expiration date and the clinical study number.

For Use in Clinical Study CR-6013 Only Not For Sale Product Conforms with CE Mark Requirements
 
Content: 10 ml of artificial tears (eye drops) for the treatment of dry eye symptoms.
 
Sponsored by: Johnson & Johnson Vision Care, Inc. [name], USA
 
   
 
LOT:                      EXP:                      RC:
		
---	--	--

